Prehabilitation of Frail Surgical Cancer Patients using Remote Ischemic Preconditioning

NCT03853473

Date of Document: December 6th, 2019

Purpose:

Remote ischemic preconditioning (RIPC) was first described three decades ago as an intervention to protect vital organs from ischemic injury. RIPC occurs when a tissue is made transiently ischemic (5 minutes) for repeated bouts (5 times) prior to the longer ischemic insult. Recently it has been shown exercise performance and motor function are improved in young, healthy individuals when RIPC is performed on the arm or leg using a simple blood pressure cuff to occlude blood flow to the limb. The application of RIPC to individuals with reduced functional capacity, however, is largely unexplored. [name] group was the first to apply RIPC to chronic stroke survivors with reduced physical function, and two weeks of RIPC increases walking speed, paretic muscle strength and fatigue resistance. Advanced age and cancer are both dramatic accelerators of frailty and frail patients have poor surgical outcomes. Therefore, we propose to apply this non-invasive, simple intervention as a "prehabilitative" therapy to elderly patients with colon cancer during the perioperative period.

Previous Findings and Pilot Data:

RIPC is a safe, well-tolerated, cost-effective, and easy to administer stimulus that has been shown to improve motor function and muscle performance in healthy individuals. [name] work in chronic stroke survivors with low physical function demonstrates that two weeks of RIPC improves muscle strength and increases self-selected walking speed. Exercise prehabilitation programs have shown positive effects on physical function in the preoperative period in patients scheduled for abdominal surgery; however elderly, frail colon cancer patients may not have the capacity to exercise at intensities required to derive physiological benefit, and adherence to exercise programs is generally low. The effects of RIPC to improve functional capacity in elderly frail cancer patients is unknown, as is the application of RIPC as a prehabilitative intervention prior to surgery in the elderly.

Hypothesis and Aims:

We hypothesize that daily RIPC for 2 weeks will decrease frailty in elderly colon cancer patients prior to surgery.

Specific Aim 1: Determine the efficacy of RIPC to decrease frailty in the preoperative period. RIPC will decrease frailty as evidenced by increased 6MWT distance in pre-surgical colon cancer patients compared to standard of care colon cancer patients.

Specific Aim 2: Investigate whether RIPC improves functional recovery postoperatively. Frail colon cancer patients who undergo RIPC in the preoperative period will exhibit decreased frailty assessed by the 6MWT 4-weeks postoperatively compared to standard of care patients.

Inclusion Criteria:

- be between ages of 55-85
- have a diagnosis of non-metastatic colon cancer
- be scheduled for curative resection of non-metastatic colon cancer

Exclusion Criteria:

- condition which prevents walking
- any condition in which compression of the arm or transient ischemia is contraindicated (e.g. wounds in the arm)
- neurodegenerative disorder
- unstable angina in previous month
- MI during previous month

Procedures:

1. A member of the study team will pre-screen patients who fit the study criteria by looking at the clinical schedules of Drs. [name], [name] and [name] daily in Epic
2. When a potentially eligible patient is identified via Epic, the study team member will contact Drs. [name], [name] and [name] via email prior to the clinic visit. If the patient is identified as a surgical candidate by the surgeon, the surgeon will introduce the study team member to the patient at the conclusion of their surgical consult visit.
3. The study team member will explain the study to the patient in an unoccupied consult room in the colorectal surgery clinical area and obtain written informed consent if the patient is interested.
4. After obtaining consent, the next contact the study team will have with the patient will be in-person at the patient's preadmission testing (PAT) visit (standard of care for colon cancer patients), which will be approximately 3 weeks prior to planned surgery. At the conclusion of the patients PAT clinical visit, a study team member will measure 1) 10 meter walk test, 2) 6 minute walk test, 3) handgrip strength, 4) timed up and go test. These measures will all either be collected in the hallway of the PAT clinic area, or in the case of handgrip and timed up and go, in an unoccupied consult room. The time to conduct all tests is approximately 15-20 minutes.
5. If the patient's 6-minute walk test distance is <80% of their age predicted distance [Predicted distance in 6 minutes (meters) = $868 - (\text{age} \times 2.9) - (\text{sex} \times 74.7)$ where age is in years and "1" is assigned for females and "0" is assigned for males.], they will continue in the study. If their 6-minute walk test distance is >80% of their age predicted norm, they will not be considered "frail" and will be excluded from the study.
6. After baseline measures of frailty are collected, the study participants will be randomized to receive either remote ischemic preconditioning (RIPC) or standard of care
7. Participants in the RIPC group will be given a handheld blood pressure cuff and instructions how to perform the RIPC procedure at home, daily, until their follow-up appointment prior to surgery
8. A member of the study team will call the study participants in the RIPC group 2-3 times to monitor compliance with the intervention.

9. Within 4 days of planned surgery, all participants will return to Froedtert Hospital and have their 6-minute walk test, 10 meter walk test, handgrip strength and timed up and go test re-evaluated at the 2nd floor Outpatient Rehabilitation Gym (Room 2112) by a member of the study team. This will be the conclusion of the intervention period for patients in the RIPC group.
10. Blood pressure variability data from the surgical procedure will be acquired from the anesthetic record
11. Participants will return to the 2nd floor Outpatient Rehabilitation Gym approximately 4 weeks after surgery to have the 10-meter walk test, 6-minute walk test, handgrip strength, and timed up and go test re-evaluated by a member of the study team. This will complete all study procedures.

Individual Procedures:

1. Remote Ischemic Preconditioning (RIPC): A handheld sphygmomanometer (Hokason DS400) and blood pressure cuff (Hokanson SC12) will be given to study participants in the RIPC group. To perform RIPC, the cuff will be inflated to 225 mmHg for 5 minutes on the non-dominant upper arm, then released for a 5-minute recovery period. Five cycles of inflation/recovery will be performed daily. Each participant must demonstrate competence completing a single cycle of inflation/deflation independently to continue with the study. To monitor compliance, participants must complete daily log sheets documenting the time and maximum pressure of each cuff inflation. The research coordinator will also place phone calls on days 3, 7 and 10 after baseline testing to ask if all sessions to date have been completed.
2. 6-Minute Walk Test (6MWT): The 6MWT is a submaximal test that evaluates the integrated responses required during exercise, has been validated in colorectal surgery patients, evaluates endurance during a moderate-intensity task, and predicts recovery after elective colon resection surgery. We will administer the 6MWT in accordance with guidelines set by the American Thoracic Society. For baseline evaluation, after a 10 minute rest, participants will walk down a 50 meter hallway marked in 3 meter increments in either the Preoperative Testing Clinic or 2nd floor Outpatient Rehab Gym at a pace they feel would be tiring after 6 minutes. The hallway will be marked with cones at the turnaround points, laps will be counted with a lap-counter, and the test administrator will ensure no one talks to the participant or crosses their path during the test. Participants will be told to pivot around the cones as quickly as possible and that they can slow down, rest, or stop as needed. Participants will rate their level of fatigue before and after the walk using the 10-point Borg scale of perceived fatigue. After baseline testing, the percent of age- and sex-specific predicted distance will be calculated using the following equation:

Predicted distance in 6 minutes (meters) = $868 - (\text{age} \times 2.9) - (\text{sex} \times 74.7)$ where age is in years and "1" is assigned for females and "0" is assigned for males.⁴⁸

Since our goal is to examine the effects of RIPC on frail colon cancer patients, only participants who cover a distance $\leq 80\%$ of the age- and sex-predicted norms will be included in the study. Others have shown that pre-surgical colon cancer patients walk 65 – 74% of age- and sex-specific norms during the 6MWT.

3. 10 Meter Walk Test (10MWT): The 10 MWT is a validated measure to assess self-selected walking speed, considered by some the "6th vital sign". Slow walking speed has also been identified as one of five metrics which identify frailty, and is a strong predictor of adverse outcomes associated with frailty. In a hallway, participants will walk at their comfortable speed for 20 meters and be timed during meters 5-15 using a stopwatch to assess steady-state walking. 10MWT measures will be done in triplicate.

4. Handgrip Strength (HGS): Weak HGS has also been identified as a metric to identify frail patients. Patients with weak HGS are six times more likely to be frail, and HGS positively correlates with self-perceived fatigue, disability, morbidity, and mortality. Participants will squeeze a hydraulic hand dynamometer as hard as they can three times with their dominant hand and the maximal force generated will be recorded.

5. Timed up and Go (TUG): TUG is the time it takes a person to stand from an armed chair, walk three meters, turn around, walk back, and sit back down. Increased time during the TUG test has also been shown to be a sensitive and specific measure of frailty in elderly patients.

6. Intraoperative Blood Pressure Variability: We will query the Clinical Research Database Warehouse at the Medical College of Wisconsin and intraoperative blood pressure measurements will be extracted for each study participant. No other patient identifiers or clinical data will be revealed. BPV will be assessed as the product of magnitude x duration of SBP excursions outside the SBP range (>135 mmHg or <95 mmHg; area under the curve).

Statistical Analysis:

All statistical analysis will be overseen by [name], Ph.D. (Co-I). Randomization of frail, pre-surgical colon cancer patients to the two intervention groups will be performed by [name] using randomized block designs (randomly chosen block sizes of 3, 6 and 9). [name] will work directly with a member of the study team. When a study participant is enrolled, he or she will receive a sequential number which will have a randomization schedule assigned to it (i.e. no intervention or RIPC), and this will be communicated to the study team.

Statistical analysis for the primary study outcome, the change in 6-minute walk test distance in the pre-surgical period, will be based on the analysis of covariance model

(ANCOVA) with two predictors: group membership (RIPC vs. no intervention control) and the baseline value of 6MWT. To investigate power properties, we used a two-sample t-test (under the assumption that there will be no baseline effect of 6MWT). We plan to enroll 48 patients per group, but expect that 6 patients will be lost to follow-up based on an estimated attrition rate of 10-15% during the preoperative period. Thus, 42 patients will be available for comparing the intervention (RIPC) and control groups. Power calculations for a two sample t-test on 40 patients per group show that we will be able to detect a change in 6MWT distance of 30 meters from baseline to 48 hours pre-surgery between the groups with 82% power (SD=46 meters from literature review). A difference of ≥ 30 meters between the RIPC and standard of care groups is in agreement with previous work done by Gillis and colleagues which examined the effect of exercise prehabilitation on pre-surgical colon cancer patients and showed a difference in 6MWT distance of 41.6 meters between the exercise prehabilitation and standard of care groups. We will apply variance stabilizing transformations (natural logarithm or square root) to make ANCOVA residuals more normal if needed. If these transformations are not sufficient, we will proceed with a Mann-Whitney test. When we add 5% to 40 (asymptotic relative efficiency of Mann-Whitney to t-test is 96% under normality), then the Mann-Whitney test (a nonparametric alternative to the two-sample t-test) with 42 subjects per group will have similar statistical power when data comes from a normal distribution. We will use the same models for our pre-surgery secondary outcomes of self-selected walking speed during the 10-meter walk test, handgrip strength, and timed-up-and-go time.

The analysis of changes in 6MWT from pre-surgical values to 4-weeks post-surgery will be conducted relying on variance stabilizing transformations and ANCOVA; however, the power calculations change. We expect to lose approximately 5 subjects per group from the test conducted 48-hours prior to surgery to 4-weeks post-surgery and have planned for 37 subjects per group at 4 weeks after surgery. At 35 subjects per group for t-test and 37 per group for Mann-Whitney test, the detectable difference in 6MWT distance at 82% power between the groups is 0.7 standard deviations. Based on others work in post-surgical colon cancer patients showing a SD of 46 meters, we expect to detect a difference between the groups of ≥ 32 meters. We will use the same models for our post-surgery secondary outcomes of self-selected walking speed during the 10-meter walk test, handgrip strength, and timed-up-and-go time.

We will explore the distribution of intraoperative blood pressure variability as measured by area above or below 135 mmHg or 95 mmHg, respectively and apply variance stabilizing transformations. There is no baseline value to adjust for in this analysis. At 40 subjects per groups for t-test and 42 per group for the Mann-Whitney test, the detectable difference at 76% power between the groups is 0.6 standard deviations, and at 0.7 standard deviations difference the power will be 87%. If the number of subjects with all blood pressure data between the upper and lower boundaries (meaning blood pressure variability = 0) is higher than 5, we will rely on exact Mann-Whitney test.

Risks:

1. Remote Ischemic Preconditioning (RIPC): there is a risk that the repeated occlusions of blood flow to arm during the RIPC protocol may cause tingling and numbness in the arm or hand during the cuff inflation period which may be uncomfortable for the study participants.
2. Clinical test of frailty: Study participants may feel tired during the 6MWT and there is a risk that patients could fall during either the 6MWT, 10 meter walk test, or timed up and go test (TUG).
3. Adverse event during 6MWT: there is a small chance that study participants could have a cardiovascular event during the 6MWT.
4. Loss of confidentiality

Safeguarding Against Risks:

1. RIPC: any discomfort related to the occlusion of blood flow to the arm during the RIPC should be minor and transient based on our experience performing the protocol. Based on our experience performing the procedure, and a multitude of other studies which have performed RIPC, we do not anticipate any issues with study participants performing the procedures at home.
2. Clinical tests of frailty: There is a very minimal risk of falling during the walking tests or the timed up and go test. The test administrators will provide contact guard assistance as needed and a gait belt can be worn by participants if deemed necessary by study staff. Participants may feel fatigued during the 6- minute walk test. All participants will be instructed to proceed at their own pace, and there will be chairs at both ends and in the middle of the hallway where the test is being conducted so participants can sit and rest if needed.
3. Adverse event during 6-minute walk test: Although risk of a sudden cardiac event in response to moderate intensity exercise (50-60% target heart rate) in elderly colon cancer patients is relatively rare, we have taken several measures to safeguard the health of our participants. First, all participants will be carefully screened by the PIs or their physician (Drs. [name], [name] or [name]) prior to exercise to determine the risk of an adverse response to exercise (e.g. uncontrolled hypertension or elevated resting vital signs). Blood pressure and resting heart rate will also be measured by [name] (clinical research assistant) immediately prior to beginning the 6MWT. Second, we will follow the guidelines for conducting the 6-minute walk test established by the American Thoracic Society. Specifically, we will ensure participants have not had unstable angina or a myocardial infarction in the previous month, that participants resting heart rate is below 120 beats per minute, systolic blood pressure is less than 180 mmHg, and diastolic blood pressure is less than 100 mmHg. The sites of 6MWT measurements [Peroperative Testing Clinic (baseline) and 2nd floor Outpatient Rehab Gym (48 hours pre-surgery and 4-weeks post-surgery)] are equipped with Automated External Defibrillators (AEDs), have physicians present at all times, and all members of the study team are certified in basic

life support. We will immediately terminate the 6-minute walk test if participants experience any of the following: chest pain, intolerable dyspnea, leg cramps, staggering, diaphoresis, or they develop a pale or ashen appearance.

4. Loss of Confidentiality: All personal information and protected health information will be collected and stored in a locked file cabinet in [name] office. Only necessary research staff will have access to the personal information collected from the patients and access will be supervised by [name]. Each participant will be assigned a code and the data will be filed according to code.

Informed Consent:

The informed consent process will take place in the Colorectal Surgery Clinic at Froedtert Hospital. We will allow a minimum of 15 minutes to go through the consent and answer any questions. The minimum time between the informed consent process and the beginning of project related procedures will vary for each participant, and this will depend on the time and date of their scheduled surgery. The first project related procedure will occur 2-3 weeks prior to the participant's scheduled date of surgery.

Throughout the informed consent process, the study team member will continuously ask if the subject has any questions or concerns. The study team member will verbally stress the right of the individual to stop at any time, and that stopping will not negatively impact the medical care they are receiving.

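### The cuff-competence rule can remove RIPC participants after randomisation, and nothing says they are followed and analysed as randomised

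*Combined protocol and SAP*

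**What the plan says.** The rule is in Individual Procedures, item 1 (RIPC): "Each participant must demonstrate competence completing a single cycle of inflation/deflation independently to continue with the study". It gives no time for the check, no number of attempts and no handling of failures. The preceding sentences of that item describe equipment given to the RIPC group and how it is used.

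The order of events under Procedures is:
- Step 4, baseline: the study team "will measure 1) 10 meter walk test, 2) 6 minute walk test, 3) handgrip strength, 4) timed up and go test". No cuff test is listed.
- Step 5: those below 80% of predicted 6MWT distance pass the screen, and "they will continue in the study"; those above it are excluded.
- Step 6: "After baseline measures of frailty are collected, the study participants will be randomized to receive either remote ischemic preconditioning (RIPC) or standard of care".
- Step 7: "Participants in the RIPC group will be given a handheld blood pressure cuff and instructions how to perform the RIPC procedure at home".
- Step 9: "Within 4 days of planned surgery, all participants will return".

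Cuff competence is not among the Inclusion or Exclusion Criteria. Statistical Analysis describes those allocated only as follows: "Randomization of frail, pre-surgical colon cancer patients to the two intervention groups". It specifies an ANCOVA on group and baseline 6MWT. It allows for 6 losses per group before surgery, described as loss to follow-up, and names no analysis population.

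**The concern.** The condition is attached to staying in the study, not merely to using the cuff at home. Step 5 uses almost the same phrase as the opposite of exclusion, so failing the check reads as removal. Because the check belongs to the RIPC procedure and the cuff is issued after allocation to that arm alone, the removal would be post-randomisation and one-sided.

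The remaining RIPC participants would then be a selected group compared with unselected controls. Randomisation would no longer protect the pre-surgical 6MWT comparison, the 4-week comparison, or the secondary outcomes that use the same models. Adjusting for baseline 6MWT removes only the selection that baseline walking distance explains. Differences in dexterity, cognition or motivation would remain. It is also unclear whether competence failures are counted within the 6 expected losses or come on top of them.

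**Working it through.** **Inputs from Statistical Analysis.** SD 46 m; target difference 30 m; 48 enrolled and 42 available per group; power quoted at 40 per group; 37 per group planned at 4 weeks, with a detectable difference of 32 m.

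**Assumptions not in the documents.** Two-sided alpha of 0.05; failure fraction f in the RIPC arm; residual correlation r between competence and 6MWT change beyond baseline.

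**The plan's own figure.** Noncentral-t power at 40 vs 40, 30 m, SD 46 m is 82.1%, against 82% stated. It reproduces.

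**Selection bias with no true effect.** Competence is treated as a latent normal variable, and the lowest fraction f of the RIPC arm is removed. With z_f the normal quantile of f and φ the normal density:
- bias = r × 46 × φ(z_f) / (1 − f)
- SE = 46 × √(1/(42(1 − f)) + 1/42)
- type I error = P(|Z + bias/SE| > 1.96)

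Worked example, f = 10%, r = 0.3: φ(z_f) = 0.1755, so bias = 0.3 × 46 × 0.1755/0.9 = 2.7 m. SE = 46 × √(1/37.8 + 1/42) = 10.3 m. The type I error is 5.8%.

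| f | r | Bias | Share of 30 m | Type I error |
|---|---|---|---|---|
| any | 0 | 0 m | 0% | 5.0% |
| 1% | 0.3 | 0.4 m | 1% | 5.02% |
| 2% | 0.3 | 0.7 m | 2% | 5.05% |
| 5% | 0.3 | 1.5 m | 5% | 5.2% |
| 10% | 0.3 | 2.7 m | 9% | 5.8% |
| 15% | 0.5 | 6.3 m | 21% | 9.3% |

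The last row is an extreme case, not an expectation. A negative r reverses the sign of the bias and leaves the error rate unchanged. At 4 weeks (37 per arm), f = 10% with r = 0.3 gives 5.7%, and the extreme case gives 8.7%. The implied gap in mean 6MWT change between those who pass and those who fail is 27–37 m at r = 0.3 for f = 1–10%, and 42 m in the extreme case.

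**Check with the planned model.** Simulated ANCOVA with the baseline covariate, 20,000 runs each:
- f = 2%, r = 0.3: 0.7 m, 5.2%
- f = 10%, r = 0.3: 2.7 m, 5.5%
- f = 15%, r = 0.5: 6.4 m, 8.9%
- f = 10%, competence related only to baseline 6MWT: 0.0 m, 4.7%

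**Loss of numbers.** If 10% fail in addition to the 6 expected losses, about 42 × 0.9 = 38 RIPC participants remain. Power for 30 m is 82.0% at 42 vs 38, against 84.0% at 42 vs 42. Lost power is a minor issue; the concern is bias.

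**The case against.** The rule is one sentence and can be read otherwise. It speaks of each participant and gives no time, so a check of everyone before randomisation is not strictly ruled out. It could also be a training standard, with coaching until the participant succeeds, in which case almost nobody would be removed. Step 9 brings all participants back, whereas steps 7 and 8 name the RIPC group when only that arm is meant. No passage says that a randomised person is dropped from analysis.

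Failure may well be rare. The background section says that "RIPC is a safe, well-tolerated, cost-effective, and easy to administer stimulus", Safeguarding Against Risks anticipates no problems at home, and the exclusion of neurodegenerative disorders and of arm-compression contraindications removes some likely failures. Even r = 0.3 requires a pass/fail gap about as large as the whole target effect. At r = 0.1 (a gap of about 9–12 m) the bias is only 0.1–0.9 m. Keeping those who fail also costs power through dilution.

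The points on size stand: the bias may be close to zero. The points on reading do not remove the defect. No step places a cuff check before randomisation, and controls are never given a cuff. Step 9 does not settle the matter, because someone who may not continue need not be among those who return. If a check of everyone beforehand was intended, the eligibility criteria omit it and the text still needs correcting. The dilution cost is real and is set out with the fix.

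**Conclusion.** The concern holds. On the natural reading, the plan allows removal from one arm after randomisation, and neither the follow-up steps nor the analysis section repairs this. Confidence in that reading is medium, because the sentence states neither when nor in whom competence is checked.

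The documents establish neither the size nor the direction of the bias. It is about zero if failure is rare or if competence is related only to baseline 6MWT, and otherwise it can go either way. Under the assumed range of 1–10% failing and a residual correlation of 0 to 0.3 in either direction, it is at most 2.7 m, and the type I error is at most 5.8%. These figures illustrate and do not predict. The point should be fixed because the stated rule weakens the comparison if it is followed and the correction is simple.

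**What to change.** Keep the competence check but separate it from study participation. State when it is done and in whom, and replace the condition on continuing with wording such as: *All randomised participants, whatever the result of this check, attend the pre-surgical and 4-week assessments and are analysed in the arm to which they were randomised; the number failing is reported.* The sponsor should state separately what the check governs for home cuff use. A sensitivity analysis for those without a pre-surgical 6MWT is optional.

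**Cost.** About 0–5 of 48 RIPC participants (48 × 0.01 to 48 × 0.10) are kept for two visits already scheduled. If those who fail gain nothing, the difference shrinks to 30 × (1 − f):
- Pre-surgical, 42 per arm: power falls from 84.0% to 82.5% (29.4 m), 80.1% (28.5 m) or 75.7% (27.0 m) at 2%, 5% or 10% failing.
- 4 weeks, 37 per arm: starting from 32 m, power falls from 83.9% to 80.1% (30.4 m) or 75.7% (28.8 m) at 5% or 10% failing.

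At 5% or more failing, power is below the planned 82%. That is the price of estimating the effect of assignment.

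**Alternative.** Do the check in all candidates before step 6 and list it as an eligibility criterion. This avoids dilution. It takes a few extra minutes per candidate, adds one cuff cycle in future controls, and limits the population to people who can use the cuff. Reaching 96 randomised needs 96/(1 − f) − 96 further frail candidates: about 1, 5 or 11 at 1%, 5% or 10% failing.

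### During home RIPC, the visible plan has no scheduled contact that asks about a new arm problem and no rule for holding the cuff before the visit that ends treatment

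*Combined protocol and SAP*

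**What the plan says.** The Exclusion Criteria rule out "any condition in which compression of the arm or transient ischemia is contraindicated (e.g. wounds in the arm"). Arm condition is therefore, in the plan's own terms, a reason not to apply the cuff.

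After randomization, RIPC participants take the cuff home and use it daily until the pre-surgical visit (Procedures, step 7). At each inflation "the cuff will be inflated to 225 mmHg for 5 minutes on the non-dominant upper arm", with five cycles a day (Individual Procedures, item 1). The same item describes three kinds of oversight:

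- **Demonstration.** Each participant must show that they can complete one inflation and deflation unaided.
- **Log.** The requirement is that "participants must complete daily log sheets documenting the time and maximum pressure of each cuff inflation".
- **Calls.** The coordinator makes "phone calls on days 3, 7 and 10 after baseline testing to ask if all sessions to date have been completed". Procedures, step 8, describes them as calls made "2-3 times to monitor compliance with the intervention".

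The next study visit is the retest within 4 days of planned surgery, and RIPC ends there (Procedures, step 9). Risks, item 1, names tingling and numbness while the cuff is inflated. Safeguarding Against Risks, item 1, expects any discomfort to be slight and short-lived and foresees no difficulty with home use.

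**The concern.** The calls and the log are set up to measure compliance. A participant who skips sessions because of an arm problem will answer no on a call and may be found that way. A participant who completes every session despite a new wound under the cuff, or despite numbness that persists between sessions, will answer yes. That person is found only by volunteering the problem. Both conditions fall outside the short-lived discomfort that the plan expects.

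The supervised 6MWT is handled differently. Safeguarding Against Risks, item 3, gives heart-rate and blood-pressure limits before the test and a list of symptoms that stop it. The visible text has no counterpart for unsupervised inflations to 225 mmHg in patients aged 55 to 85 who are selected as frail. What is at stake is patient safety, at a minor level. Sample size, power and analysis are not affected.

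**Working it through.** The plan states no figure on this point, so there is none to reproduce. The check has two parts.

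**1. Each stated contact or record after randomization, set against the arm question**

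| Contact or record | Stated content | Arm wound or persistent numbness asked about? |
|---|---|---|
| Single-cycle demonstration | Competence with the cuff | Not stated; a problem already present might be noticed |
| Calls (days 3, 7, 10; step 8 says two or three) | Whether sessions were completed | Not stated |
| Daily log | Time and maximum pressure | Not stated |
| Pre-surgical retest | Four functional tests, with blood pressure and heart rate before the 6MWT | Not stated; RIPC ends here in any case |

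The gap therefore concerns problems that begin after the demonstration and before the retest. No section gives a rule for holding RIPC.

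**2. Exposure, and what a question on the calls would change**

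Inputs: five inflations of 5 minutes a day (Individual Procedures, item 1); a 14-day course, from "daily RIPC for 2 weeks" (Hypothesis and Aims); calls on days 3, 7 and 10; 48 RIPC participants (Statistical Analysis). I assume that RIPC starts at baseline and that the retest falls on day 14.

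- Exposure per day: 5 × 5 = 25 minutes of occlusion.
- Exposure per course: 14 × 5 = 70 inflations; 14 × 25 = 350 minutes.
- As written, a problem starting on day 1 could run through all 70 inflations without a stated contact asking about it.

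If each call carried the question, the longest wait until the next call or the end of treatment would be:

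| Calls made | Intervals (days) | Longest wait | Inflations in that wait |
|---|---|---|---|
| Days 3, 7, 10 | 3, 4, 3, 4 | 4 days | 4 × 5 = 20 (20/70 = 29%) |
| Days 3, 7 | 3, 4, 7 | 7 days | 7 × 5 = 35 (35/70 = 50%) |
| Days 3, 10 | 3, 7, 4 | 7 days | 35 |
| Days 7, 10 | 7, 3, 4 | 7 days | 35 |

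Calls in total, if every participant stays in: 48 × 3 = 144, or 48 × 2 = 96. At an assumed 15 to 30 seconds per question, 144 calls take 144 × 15 s = 36 minutes to 144 × 30 s = 72 minutes. For 96 calls it is 24 to 48 minutes.

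**Sensitivity to course length.** Procedures, step 4, places baseline at a visit "which will be approximately 3 weeks prior to planned surgery". With a retest 4 to 2 days before surgery, the course is 21 − 4 = 17 to 21 − 2 = 19 days, and 7 to 9 days follow the day 10 call. Informed Consent allows a first procedure as late as 2 weeks before surgery; the course is then 10 to 12 days, and 0 to 2 days follow that call. This range concerns when the calls fall. The point here is what they ask.

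**The case against.** The strongest reply is that this argues from silence. The protocol gives the purpose of the calls; it is not a call script and does not bar other questions. Participants receive instructions for the procedure (Procedures, step 7), and neither that sheet nor the consent pages can be seen. Either may tell participants when to stop and whom to tell. Participants are also told that they may stop at any time (Informed Consent). The contraindication is an entry criterion that the plan never undertakes to re-check, and nothing in the documents indicates how often an arm problem would arise or go unreported.

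Most of this stands, and it keeps the point small. It does not remove it. Stop advice and the right to withdraw both depend on the participant recognising a problem and raising it, whereas a question from staff does not. The calls are already scheduled.

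A reader might infer four stronger things that the documents do not support:

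- **That participants get no stop advice.** Unseen pages may contain it.
- **That the plan contradicts itself.** It never promised a re-check.
- **That the retest cannot reveal a problem in the cuffed arm,** because handgrip is measured "three times with their dominant hand". Safeguarding Against Risks, item 3, also requires blood pressure before the 6MWT, and the arm is not stated, so handgrip cannot be called the only arm measure. The retest comes too late for a different reason: RIPC ends there.
- **That 70 inflations measure risk.** They measure exposure only.

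**Conclusion.** The point holds as a minor safety improvement, to be considered. After the single-cycle demonstration, the only stated monitoring during home RIPC is two or three compliance calls and a log of time and maximum pressure. No visible text asks about a new arm wound or persistent numbness, or says when to hold the cuff, before treatment ends.

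No number of affected participants is claimed. The 4-day and 7-day waits rest on a 14-day course and on the question being asked at every call; the 4-day figure also requires all three calls, which step 8 does not guarantee. The call dates are adequate for a 14-day course, and no extra call is needed to make the point.

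**What to change.** In Individual Procedures, item 1:

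- Add one question to each existing call: *Any new wound, persistent numbness or other problem in the arm you use the cuff on?*
- State that a yes holds RIPC until the principal investigator or treating surgeon decides whether it resumes.

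In Procedures, step 8, replace two or three calls with the three calls on days 3, 7 and 10, so that the two sections agree.

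The cost is a few lines of protocol text and, under the timing assumed above, about an hour of coordinator time over the whole trial. The downside is that some sessions may be held for symptoms that prove benign, which slightly lowers the RIPC dose: each day held removes 5 of 70 inflations, or 7% of a 14-day course.
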